7.3.4. Best Overall Response

Best overall response for each participant is defined as best response during the course of the study (best in the categories of CR or PR), including responses at unscheduled visits.

Participants without a BOR (ie, participants not achieving a response of either CR or PR) in the treatment phase will be considered as nonresponders for BOR in the responder analysis. Number and percentage of participants in each best response category will be tabulated by treatment group.

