Chronic GVHD staging and grading will be assessed using NIH consensus guidelines (Lee et al 2015, Jagasia et al 2015); safety and tolerability will be assessed as per NCI CTCAE v4.03.

Telephone conferences with study investigators will be scheduled by the sponsor in order to review cohort-specific data and overall safety data, to adjudicate individual high-grade AEs as potentially dose-limiting, and to guide other major study decisions.

An analysis to determine the dose and schedule for Part 2 will be performed once the last participant completes at least 3 months of study treatment (see Section 6.1.1.4). An external DMC will review the data from this analysis and provide a recommendation on an appropriate dose for Part 2.

Participants who are randomized to the steroids single-agent cohort may be crossed over once the appropriate dosing/schedule for itacitinib for Part 1 was determined provided the participant completed 6 months of treatment with corticosteroids alone.

4.1.3. Part 2

Part 2 will employ a randomized, double-blind, placebo-controlled design in order to assess the efficacy of itacitinib in combination with corticosteroids using the dose selected in Part 1 expansion. Randomization will be stratified by cGVHD risk status (moderate vs severe). Participants randomized to the placebo group will be permitted to cross over to the experimental group after completion of the primary analysis as appropriate. Participants will remain on study for a total of 37 months, including the treatment period, safety follow-up, and post-treatment

GVHD follow-up, unless confirmed GVHD progression, start of a new GVHD therapy, or relapse/recurrence of underlying hematologic disease occurs earlier.

GVHD staging and grading will be assessed using NIH consensus guidelines (Lee et al 2015, Jagasia et al 2015); safety and tolerability will be assessed as per NCI CTCAE v4.03.

An interim analysis for futility will be performed once 70 participants have completed the Day 180 visit; the final analysis will be performed once all participants have completed the Day 180 visit.

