7.1. General Considerations

In Part 1, all efficacy analyses will be performed using the safety run-in population. In Part 1 Expansion, all efficacy analyses will be performed using the safety population.

If there are not sufficient data for meaningful statistical inference, the planned analysis will not be performed, and only related summary statistics and/or listings will be provided.

In all efficacy analyses, initiation of new systemic anti-GVHD therapy includes 4 scenarios:

1. Initiation of new anti-GVHD therapy including a higher dose of corticosteroid than that used at Day 1.
2. The need for a second dose increase in corticosteroids.
3. A dose increase in corticosteroids that is not tapered back to the previous dose of corticosteroids within 6 weeks (\pm 2 days) of the increase.
4. Reintroduction of systemic corticosteroids that occurs after complete taper of corticosteroids due to response.

No formal statistical tests will be performed.

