7.3. Analyses of the Secondary Efficacy Parameters

7.3.1. Response Rate

Response rate at 3, 6, and 12 months (Days 90, 180, and 365) is defined as the proportion of participants who achieved a response (CR or PR) at each of these timepoints based on an ITT population.

A participant will not be considered a responder for the analysis of ORR at 3, 6, and 12 months if any of the following events occurred at or prior to the response assessment at the predefined timepoint:

- cGVHD progression per NIH response criteria or initiation of a new systemic therapy for cGVHD

- Evidence of progression of the underlying hematologic disease
- Withdrawal from the study
- Death
- Response assessment missing (not performed) at the predefined timepoint

The proportion of responders will be estimated with 95% CIs. Confidence intervals will be calculated based on the exact method for binomial distributions. Summary statistics will be provided.

Additional analyses may be performed based on evaluable subsets. An evaluable population will also be considered with participants who have completed 3, 6, or 12 months of follow-up as of the cutoff date or discontinued earlier because of new cGVHD progression. Presentations of ORR at Month 3 and Month 6 will include a footnote explaining what "evaluable" means (ie, participants who had at least 3 or 6 months of follow-up as of the cutoff date or discontinued earlier).

Summary statistics and 95% CI will be provided by cohort. The primary comparisons in Part 1 expansion will involve only the 2 itacitinib groups (Treatment Groups A and B) and the corticosteroids-only group (Treatment Group D) as a result of Protocol Amendment 8, in which Treatment Group C (300 mg BID + corticosteroids) was discontinued. Data from Treatment Group C will be presented only as summary statistics and will not be subjected to any statistical comparison.

Pairwise Cochran-Mantel-Haenszel tests will be conducted for Month 6 response rate for each of the 2 itacitinib groups (Treatment Groups A and B) and the corticosteroids-only group (Treatment Group D) as an exploratory analysis.

The secondary endpoints discussed below will be summarized by Treatment Groups A, B, and D using the ITT population for efficacy-related endpoints and all groups for safety-related endpoints.

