7.3.2. Time to Response

Time to response is defined as the interval from randomization to first response (CR or PR) before initiation of new therapy. In the time to response analysis, participants without a response after randomization will be censored at either study withdrawal, initiation of new systemic anti-GVHD therapy, death, relapse, or last response assessment prior to or on the cutoff date, whichever is earliest. Time to response will be summarized for participants who achieve a response using the Kaplan-Meier method. Median time to response and a 95% CI will be estimated.

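### Best overall response has no stated cut at new systemic therapy or crossover, and its section gives two different windows, so a response after rescue can be credited to the assigned arm

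*SAP*

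**What the plan says.** SAP 7.3.4 gives BOR two windows. The definition is the "best response during the course of the study (best in the categories of CR or PR), including responses at unscheduled visits". The next sentence says that participants without a CR or PR "in the treatment phase will be considered as nonresponders for BOR in the responder analysis". On reporting: "Number and percentage of participants in each best response category will be tabulated by treatment group". Appendix A plans three tables from this endpoint: 2.2.8 (overall), 2.2.8.1 (by organ) and 2.2.8.2 (skin sclerotic subgroup).

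The neighbouring endpoints each carry a cut:

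- **Response rate (SAP 7.3.1):** a participant is not a responder if "cGVHD progression per NIH response criteria or initiation of a new systemic therapy for cGVHD" came at or before the timepoint. Progression of the underlying hematologic disease has the same effect.
- **Time to response (SAP 7.3.2):** the event is the "first response (CR or PR) before initiation of new therapy". Participants without one are censored at new therapy or relapse, among other events.
- **Duration of response (SAP 7.3.3):** it ends at new systemic cGVHD therapy and is censored at hematologic relapse.

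SAP 7.1 defines the shared term: "In all efficacy analyses, initiation of new systemic anti-GVHD therapy includes 4 scenarios". Scenarios 2 to 4 concern corticosteroids only: a second increase; "A dose increase in corticosteroids that is not tapered back to the previous dose of corticosteroids within 6 weeks"; and reintroduction after a complete taper due to response.

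Protocol 4.1.2 adds: "Participants who are randomized to the steroids single-agent cohort may be crossed over". This applies once the itacitinib dosing has been determined and after 6 months of corticosteroids alone.

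**The concern.** BOR by arm is read as what the assigned treatment achieved. If a participant fails on that treatment, has corticosteroids increased again or starts itacitinib, and then responds, the response belongs to the later treatment. Three of the four response endpoints in SAP 7.3 protect against this for new therapy, and BOR does not.

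The planned tables could also contradict each other. Someone whose first response follows new therapy would be a responder in Table 2.2.8 and censored without response in Table 2.2.4. In Table 2.2.3 that person would have no coherent duration, because the terminating event precedes the start. Since each response category is tabulated, a PR that becomes a CR after rescue also moves a cell.

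**Working it through.** There is no plan figure to reproduce, because the point concerns a definition. The check follows each route by which a response after rescue could still be observed.

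**1. New non-steroid therapy, or corticosteroids above the Day 1 dose.** Protocol 6.1.2.4 and 7.1.1 require withdrawal from study treatment. Protocol 8.8.1 moves a participant who starts new GVHD therapy to survival follow-up, where Table 4 schedules no cGVHD response assessment. This route is mostly closed. Protocol 8.8.3 still collects GVHD assessments in survival follow-up for those who stopped treatment for a reason other than progression, so the course-of-study window is not fully sealed.

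**2. Corticosteroid changes at or below the Day 1 dose.** Protocol 6.1.2.4 says that re-escalation for a flare during the steroid taper is not treatment failure unless the Day 1 dose is exceeded or new systemic therapy is needed. A second increase, or one not tapered back in 6 weeks, is nevertheless new therapy under SAP 7.1. The participant can stay in the treatment phase and keep being assessed. Protocol 6.1.1.6 lets participants without CR or PR at Day 180 continue, if still benefiting, for up to 36 months in total. This route is open under both windows of SAP 7.3.4. Scenario 4 follows a taper due to response, so it mainly risks a PR becoming a CR.

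**3. Group D crossover.** The SAP has no rule for it. Grouping by treatment received (SAP Table 4) does not settle the matter, because that table does not say how to place someone who receives corticosteroids alone and later itacitinib. Crossover comes after dose selection and after 6 months, so the Month 3 rate and, visit windows aside, the Month 6 rate precede it. Month 12 response, time to response and BOR can be affected.

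**Illustrative size for the control arm.** Let *s* be control responders out of 35, *f* the share of nonresponders rescued or crossed over and still assessed, and *r* the share of those who respond.

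Rise in percentage points = 100 × (35 − *s*) × *f* × *r* / 35

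Inputs: *s* = 18 to 22, the control counts in SAP Table 3 (Month 6 response). The values *f* = 0.25 to 0.75 and *r* = 0.30 to 0.70 are assumptions; the documents give neither.

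- Low: *s* = 22, 13 × 0.25 × 0.30 = 0.975 participants; 0.975/35 = 2.8 points.
- Central: *s* = 20, 15 × 0.50 × 0.50 = 3.75; 3.75/35 = 10.7 points (57.1% to 67.9%).
- High: *s* = 18, 17 × 0.75 × 0.70 = 8.925; 8.925/35 = 25.5 points (51.4% to 76.9%).

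These lean high because they start from the Month 6 rate. A participant who responded at Month 3 and lost the response by Month 6 is already a BOR responder and cannot be added again. Month 6 nonresponders also include deaths, withdrawals, progressions and relapses (SAP 7.3.1), many of whom could not be rescued and assessed. The formula leaves out PR-to-CR upgrades, which move categories but not the total.

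**The case against.** The best defence is that SAP 7.3.4 never says a response after rescue counts. Its second sentence refers to the treatment phase, SAP 7.1 defines new therapy for all efficacy analyses, and the protocol's withdrawal rules remove most assessments after new therapy. Much of this stands: the text is silent and inconsistent, and does not decide to credit rescued responses. It does not remove the problem. SAP 7.1 defines the term without attaching any consequence for BOR, and the treatment-phase window still contains the corticosteroid events in step 2.

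Four stronger readings are tempting, and the documents do not support them:

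- **That response rate and time to response exclude responses after crossover while BOR includes them.** Neither SAP 7.3.1 nor 7.3.2 names crossover. They exclude it only if starting itacitinib is read as new systemic therapy. The clear contrast is on new therapy.
- **That the gap favours control throughout.** Crossover is confined to Group D, but corticosteroid changes can occur in every arm, and nothing shows that they are more frequent in Group D.
- **That disagreement with Month 6 response is itself a fault.** Best-ever and fixed-timepoint response differ by construction.
- **That unscheduled visits should be dropped.** Their use is prespecified and the protocol permits them. In an open-label study they could be used unequally, but no such difference is shown, and limiting BOR to scheduled visits is a preference.

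**Conclusion.** The point holds as a gap in the definition, and it is minor. SAP 7.3.4 gives two windows, and neither stops at new systemic therapy, unlike 7.3.1 to 7.3.3. Responses after scenario 2 to 4 corticosteroid changes, or after Group D crossover, can therefore enter the assigned arm's count in Tables 2.2.8, 2.2.8.1 and 2.2.8.2.

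The size cannot be derived from the documents. The range of about 3 to 25 points for the control arm rests wholly on the assumed *f* and *r*, and a reader should not take any single value in it as an estimate.

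The consequence is limited. BOR appears in no objectives table, SAP 7.1 plans no formal tests, and dose selection rests primarily on adverse events (SAP 7.2), with Month 3 and Month 6 response in support. Crossover cannot affect BOR at dose selection. It can affect later summaries.

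**What to change.** Amend the SAP text in two places.

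1. **SAP 7.3.4:** define BOR as the best CR or PR from randomization up to the earliest of new systemic therapy as defined in SAP 7.1, cGVHD progression, relapse of the underlying hematologic disease, or crossover to itacitinib. Use this one window in both sentences. Unscheduled visits inside it may stay as prespecified.
2. **SAP 7.3.1 (Month 12) and 7.3.2:** state the same crossover cut, so that all the response endpoints treat a Group D participant who starts itacitinib alike.

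The cost is a few sentences and a date condition in the programming of the affected tables. No new data are needed: the protocol already requires treatment changes for flares, new cGVHD therapy and relapse to be recorded in the eCRF (8.2.2 and 8.2.3), and SAP 6.4 already derives the itacitinib start date.

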7.3.5. Overall Survival

Overall survival is defined as the interval between the date of randomization and the date of death due to any cause. Date of death will be determined using the Death Report, the Survival Follow-Up, and the Subject Status CRFs. The Kaplan-Meier method will be used to estimate the survival time distribution and the median survival, if it is applicable. Participants with no observed death or loss to follow-up will be treated as censored at their last date known to be alive. The 95% CI will be calculated using Brookmeyer and Crowley's method (1982). Summary statistics will be provided.

7.3.6. Nonrelapse Mortality Rate

Nonrelapse mortality is defined as the time from date of randomization to date of death not preceded by underlying disease relapse/recurrence. Underlying disease relapse/recurrence is considered a competing event. If a participant is not known to have died or experienced the competing event, then NRM will be censored at the latest date the participant was known to be event-free (on or before the cutoff date). Cumulative incidence of NRM and derived probabilities at Months 3, 6, and 12 will be estimated, considering underlying disease relapse/recurrence as a competing event.

7.3.7. Relapse Rate of Malignant and Nonmalignant Hematologic Diseases

Relapse rate of malignant and nonmalignant hematologic diseases is defined as the proportion of participants whose underlying disease relapses. Relapse rate of malignant and nonmalignant hematologic diseases will be provided with a 95% CI. The CI will be calculated based on the exact method for binomial distributions. Cumulative incidence rate and summary statistics will be provided.

7.3.8. Time to Primary Hematologic Disease Relapse

Time to primary hematologic disease relapse is defined as the interval between the date of randomization and the date of relapse. Time to the relapse will be assessed using Kaplan-Meier method. Median time to relapse and a 95% CI will be estimated. Summary statistics will be provided.

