2.3.2.3. Preliminary Results for Part 1 Expansion

Preliminary data from the Part 1 expansion was reviewed ad hoc by an independent DMC. At the data cutoff date for the ad hoc DMC review (09 JUL 2021), 107 participants had been enrolled in the Part 1 expansion portion of the study in the 300 mg QD dose cohort (Treatment Group A; n = 32), 400 mg QD dose cohort (Treatment Group B; n = 25), 300 mg BID dose cohort (Treatment Group C; n = 24), and corticosteroid monotherapy dose cohort (Treatment Group D; n = 26). The median duration of exposure was 83 days (range: 2-579 days) across the itacitinib treatment groups. At the time of the data cutoff, 62 participants remained on treatment across the 4 treatment groups.

Malignancy relapse was the most frequent reason for discontinuation in Treatment Group C (itacitinib 300 mg BID in combination with corticosteroids). Although no interim analysis was planned, and the number of participants was small, with 4 confirmed relapses reported in this cohort versus 1 relapse in each of the 300 mg QD and 400 mg QD cohorts and no relapse in the corticosteroids alone cohort, the sponsor had decided, following the DMC recommendation, to discontinue the itacitinib 300 mg BID study arm.

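### SAP 7.3.8 estimates time to hematologic relapse by Kaplan-Meier with no rule for death without relapse, which does not match the competing-risk treatment in SAP 7.3.6

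*SAP*

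**What the plan says.** SAP 7.3.8 makes relapse the only event: "Time to primary hematologic disease relapse is defined as the interval between the date of randomization and the date of relapse". The estimator follows: "Time to the relapse will be assessed using Kaplan-Meier method", with a median and its 95% CI. The section does not mention death and has no censoring rule.

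SAP 7.3.6, on non-relapse mortality, takes the other approach: "Underlying disease relapse/recurrence is considered a competing event". It asks for cumulative incidence at Months 3, 6 and 12 and states a censoring date. SAP 6.4 also lists death as a competing risk for the corticosteroid-reduction summaries.

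SAP 7.3.7 covers the relapse rate. It plans a crude proportion with an exact CI and adds: "Cumulative incidence rate and summary statistics will be provided". It names no competing event and no time points. In SAP Appendix A the relapse rate goes to Table 2.2.5 and time to relapse to Table 2.2.6, so both will be reported.

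**The concern.** A participant who dies without relapse can no longer relapse. A Kaplan-Meier analysis whose only event is relapse has no place for that death except among the censored observations. It then estimates the probability of relapse in a setting where nobody dies first.

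Two outputs are affected. The relapse probabilities would not be on the same basis as the NRM probabilities from SAP 7.3.6, so the two would not add up to the probability of relapse or death. The median would be reported as a time by which half of participants relapse, even where fewer than half ever would. If SAP 7.3.7 is carried out as a proper competing-risk estimate, Tables 2.2.5 and 2.2.6 could also show different relapse probabilities for the same participants.

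Relapse is not a minor endpoint here. It was the safety concern behind stopping the 300 mg BID group, and it still bears on the choice between Groups A and B.

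**Working it through.** **Counts in the documents.** Protocol 2.3.2.3 gives group sizes at the 09 JUL 2021 cutoff of A 32, B 25, C 24 and D 26. Their sum is 32 + 25 + 24 + 26 = 107, as stated. Relapses were C 4, A 1, B 1 and D 0. The crude proportions with exact 95% CIs are:

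- A: 1/32 = 3.1% (0.1 to 16.2)
- B: 1/25 = 4.0% (0.1 to 20.4)
- C: 4/24 = 16.7% (4.7 to 37.4)
- D: 0/26 = 0% (0 to 13.2)

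The documents state no relapse probability or power for this endpoint, so there is no planned figure to reproduce beyond the total of 107.

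**Direction.** At each relapse time both estimators apply the same relapse hazard. Kaplan-Meier multiplies it by the proportion not yet relapsed with deaths removed. The cumulative incidence multiplies it by the proportion alive and relapse-free, which cannot be larger. So one minus Kaplan-Meier (1-KM) is never below the cumulative incidence. The two agree only if no non-relapse death precedes a relapse.

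**Size at 6 months.** Let R and D be the 6-month cumulative incidences of relapse and of non-relapse death, with constant hazards:

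- total cumulative hazard H = -ln(1 - R - D)
- relapse part h = H × R/(R + D)
- 1-KM = 1 - exp(-h)

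R is set to the crude proportions above. This is an illustration, because they are not 6-month estimates (median itacitinib exposure was 83 days). D is an assumption from 0% to 25%. The only NRM figure in the documents is about 18% at Month 6, from the acute GVHD Phase 3 study in Protocol 2.3.2.2.

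Example: R = 0.1667 and D = 0.18 give H = -ln(0.6533) = 0.4257, h = 0.4257 × 0.1667/0.3467 = 0.2046, and 1-KM = 18.5% against 16.7%. A simulation of 400,000 participants gave 18.5% and 16.7%.

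| Assumed 6-month NRM | 1-KM when R = 16.7% | Excess, points | Excess when R = 3.1% | Excess when R = 4.0% |
|---|---|---|---|---|
| 0% | 16.7% | 0 | 0 | 0 |
| 5% | 17.1% | 0.5 | 0.1 | 0.1 |
| 10% | 17.6% | 1.0 | 0.2 | 0.2 |
| 18% | 18.5% | 1.8 | 0.3 | 0.4 |
| 25% | 19.4% | 2.7 | 0.5 | 0.6 |

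**Growth with follow-up.** Doubling the hazards extends the same model to 12 months. With R = 16.7% at 6 months, 1-KM against cumulative incidence is 31.3% v 29.7% at NRM 5%, 33.6% v 27.6% at 18%, and 35.0% v 26.4% at 25%. These carry an illustrative early rate forward and are not forecasts.

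**A lower anchor.** Protocol 2.1 gives about 40% of chronic GVHD patients with relapse or non-relapse death within 7 years. At a constant hazard this is -ln(0.6)/7 = 0.073 per year. For a relapse share p of the total hazard, the excess is [1 - exp(-pH)] - p[1 - exp(-H)], which is largest near p = 0.5. At 12 months, H = 0.073 gives 3.58% - 3.52% = 0.06 points. The maximum is 0.25 points at 24 months and 0.54 at 36.

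**The median.** In the constant-hazard model the cumulative incidence levels off at R/(R + D). With R = 16.7% and D = 18% this is 48.1%, so no median time to relapse exists. Kaplan-Meier would still give one of about 20 months (6 × ln 2/0.2046 = 20.3). This shows the principle only. At the rates seen in Groups A and B the Kaplan-Meier median would probably not be reached.

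**The case against.** Several points against the concern stand.

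- Censoring of deaths is inferred, because SAP 7.3.8 does not state it. But other time-to-event sections (7.3.2, 7.3.3, 7.3.5, 7.3.6) give a censoring rule and this one does not, and a single-event Kaplan-Meier leaves no other place for those deaths.
- SAP 7.3.7 already promises a cumulative incidence. That helps, but it names no competing event, and it feeds a different table, so the estimate in 7.3.8 would still be reported.
- The bias is small beside the sampling error. The largest 6-month value, 2.7 points, compares with a Group C interval of 4.7% to 37.4%. If no non-relapse deaths occur, the bias is zero.

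A reader might infer three stronger things, which the documents do not support.

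- That the method inflated the relapse risk that closed Group C. Protocol 2.3.2.3 describes an ad hoc DMC review of raw counts: "4 confirmed relapses reported in this cohort versus 1 relapse in each of the 300 mg QD and 400 mg QD cohorts and no relapse" with corticosteroids alone. Kaplan-Meier cannot inflate counts, and the review's data cutoff was 09 JUL 2021, whereas SAP Amendment 1 is dated 03 MAR 2022. Group C may not receive this analysis at all, since SAP 7.3.1 limits efficacy-related secondary endpoints to Groups A, B and D.
- That a planned comparison between arms, or a published relapse curve, is distorted. SAP 7.1 plans no formal tests, 7.3.8 plans no comparison, and the only Kaplan-Meier figure in Appendix A is for failure-free survival. Descriptive estimates could still be overstated by different amounts if NRM differs by group.
- That relapse would be overstated by double-digit points at 24 months. Such figures come from projecting a crude 4/24 and an acute GVHD mortality rate at constant hazard, and the chronic GVHD figure in Protocol 2.1 points to a far smaller bias.

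**Conclusion.** The point holds as a method inconsistency with a modest effect. SAP 7.3.8 uses an estimator that, with deaths censored by implication, can only equal or exceed the actual probability of relapse, and it commits to a median without a real-world meaning. The SAP applies the competing-risk principle to NRM but not to relapse.

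At 6 months the excess is 0 to 2.7 points at 16.7% relapse and 0 to 0.6 points at 3% to 4%. These ranges rest on constant hazards, on crude proportions standing in for 6-month incidences, and on an assumed NRM of 0% to 25%. The excess grows with follow-up, and at the Protocol 2.1 background rate it would be under 0.1 point at 12 months. The Group C decision and the crude relapse counts are untouched.

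**What to change.** In SAP 7.3.8, replace Kaplan-Meier and its median with the Aalen-Johansen cumulative incidence of relapse, with death without relapse as the competing event. Report it at Months 3, 6 and 12 with 95% CIs, and use the censoring-date rule of SAP 7.3.6. In SAP 7.3.7, name the same competing event for the cumulative incidence so that Tables 2.2.5 and 2.2.6 agree. State whether Group C is included and, if so, how follow-up after the switch to 400 mg QD is handled in this analysis.

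The cost is a few sentences in the SAP. The procedure is already required for NRM, and no new data are needed.
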